## Primary Outcomes

mHealth triage tool score; physician exam determination for “needs further care” or “does not need further care”.

**Sample Size:** The preliminary triage instrument has 13 variables derived from 7 questions. A minimum sample size of 10 participants per variable per potential model outcome (either needing further care or not needing care) is required to adequately power regression analysis. Our preliminary data suggests that physician exams leading to a recommendation for further care occur for 13.7% of calls. Conservatively estimating that 10% of contacted patients will require further care, a sample size of 1300 patients in the triage cohort will be targeted.

**Data Analysis:** Data from the prospective cohort will be divided into training and validation groups (70% and 30% of the overall cohort respectively). Stepwise multiple regression with bidirectional elimination will be used on the training group dataset to build the best model for predicting physician recommendation for further care (considered as a binary outcome). Survey questions that are found not to contribute significantly to prediction will be dropped from the final triage tool. The resultant model will be applied to data from the validation cohort. To establish predictive accuracy, we will assess calibration of the model by comparing the mean error between the predicted risk and actual physician response in this cohort. Receiver operating characteristic (ROC) curves will be calculated to evaluate the discrimination of the model. As the consequences of a false-positive survey leading to unnecessary patient follow-up are minimal, whereas false-negatives may result in poor health outcomes, risk cutoffs will target a highly sensitive test with minimal false negatives. Ratings of telephone follow-up acceptability will be aggregated and summarized.

**Aim 3: Characterize the impact of timely follow-up on long-term disability and socioeconomic consequences associated with trauma in Cameroon.**

**Implementation/Data Collection:** Injured patients who are successfully contacted at any of the study time points following hospital discharge will answer an over-the-phone survey to assess disability using an augmented GOSE (aGOSE) instrument, which is a metric of multi-domain functional status initially targeted for patients following neurologic trauma. It has since been validated in diverse geographic locations and in broader clinical contexts. Additional questions to evaluate economic consequences of injury will be added to the existing GOSE instrument. As our preliminary experience indicates that respondents are extremely reticent to speak directly about money over the phone, indirect measures of economic consequences will be emphasized (**Table**). Respondents will also be asked whether they sought further care for their injuries and if so, whether care was rendered. Six months before we begin using the telephone triage tool we will collect baseline data at all 4 facilities, after which the triage tool will be implemented in a stepped-wedge fashion in the 4 facilities, staggered by three months for each facility's start date. The cohort of patients (or their surrogates) who answer the triage survey will also be asked to answer the aGOSE, which will be administered at 2-weeks and at 1, 3, and 6 months. This design will let us compare intervention patients with historical controls, while controlling for temporal trends.

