*Supplement Sample Size Calculations Adjustment:* Data collected from our prospective cohort will be divided into training and validation groups (70% and 30% of the overall cohort respectively). Our original sample size was calculated to account for a conservative prevalence of 10% of contacted patients needing further follow-up care. Based upon detecting a significant departure from 50% specificity, we estimate that we would require approximately 400 patients who are not recommended for follow-up care to be included in our validation sample. We will therefore target a sample size of 1330 trauma patients in our triage cohort. New multicenter preliminary data, however, suggest that physician exams leading to a recommendation for further care occur for 50% of contacted patients. This is a significant deviation from prior single-institution Cameroon pilot data that estimated 13.7% of contacted trauma patients would need further care. The inclusion of additional hospital sites that receive patients with more severe injuries as well as selection bias are likely contributing to this difference. If our preliminary findings remain consistent, we anticipate only requiring 220 patients not recommended for follow-up care to be included in our validation sample and 730 patients to be targeted in our triage cohort. Using a conservative estimate for our sample size calculation approach enables us to create a buffer and ensure our study is adequately powered to achieve statistical significance.

Triage tool was administered at 2 weeks with physician examination assessments from February 2020 till August 2022 (with the pauses noted above). Final 2 weeks follow-up was completed on September 14, 2022.

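### At the planned 10% prevalence, the 1300 target meets the 10-per-variable minimum only for the whole cohort; the 70% training group is expected to hold 91 cases, 7.0 per variable

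*Combined protocol and SAP*

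**What the plan says.** Section 3A, Aim 2, Sample Size counts 13 variables from the 7 triage questions and gives the sizing rule: "A minimum sample size of 10 participants per variable per potential model outcome". It says that this minimum "is required to adequately power regression analysis". It cites a pilot rate of 13.7%, takes 10% as a conservative figure, and arrives at 1300. The Protocol Summary repeats the 10% and the 1300.

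The Data Analysis paragraph that follows says: "Data from the prospective cohort will be divided into training and validation groups (70% and 30% of the overall cohort respectively". It then says which part fits the model: "Stepwise multiple regression with bidirectional elimination will be used on the training group dataset to build the best model". The other 30% is used to test the resulting model.

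The Addendum (Supplement Sample Size Calculations Adjustment) keeps the 70/30 split and restates the planning basis: "Our original sample size was calculated to account for a conservative prevalence of 10% of contacted patients needing further follow-up care". It then sizes the study on specificity in the validation sample: "We will therefore target a sample size of 1330 trauma patients in our triage cohort". It also reports newer multicentre data in which "physician exams leading to a recommendation for further care occur for 50% of contacted patients".

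**The concern.** A rule on participants per variable applies to the data on which the regression is fitted. Here that is the training group, yet 1300 is what the rule gives when every patient in the cohort is counted. A reader who takes the Sample Size paragraph by itself would conclude that at 10% prevalence the model-building step meets a minimum that the plan calls required. On the plan's own inputs it does not.

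The Aim 1 sample size text says that the overall study is powered for Aim 2, so this paragraph carries the justification for the size of the whole study. What is at stake is whether that justification is accurate. The shortfall is confined to the rarer outcome, the patients who need further care.

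**Working it through.** **Inputs.** From Section 3A, Aim 2: 13 variables; 10 participants per variable per outcome; planning prevalence 10%; pilot prevalence 13.7%; training share 70%; target 1300. From the Addendum: target 1330; newer prevalence 50%.

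**Step 1: reproduce the plan's figure.**
- Required number in each outcome group: 13 × 10 = 130.
- Cohort size at 10%: 130 / 0.10 = 1300. This matches exactly and contains no factor for the split.

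**Step 2: apply the rule to the group that fits the model, at 10%.**
- Training patients: 0.70 × 1300 = 910.
- Expected cases: 910 × 0.10 = 91, and 91 / 13 = 7.0 per variable.
- Shortfall against 130: 39 cases, or 39 / 130 = 30%.
- Expected non-cases: 910 − 91 = 819, and 819 / 13 = 63.0 per variable. Only the cases fall short.
- At 1330: 0.70 × 1330 = 931; 931 × 0.10 = 93.1 cases; 93.1 / 13 = 7.2 per variable.

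**Step 3: the other prevalences in the documents.** Training group, rarer outcome:

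| Prevalence | N | Expected count | Per variable |
|---|---|---|---|
| 10% | 1300 | 91.0 | 7.0 |
| 10% | 1330 | 93.1 | 7.2 |
| 13.7% | 1300 | 124.7 | 9.6 |
| 13.7% | 1330 | 127.5 | 9.8 |
| 50% | 1300 | 455.0 | 35.0 |
| 50% | 1330 | 465.5 | 35.8 |

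**Step 4: prevalence at which the training group meets the rule.**
- At 1300: 130 / 910 = 14.3%.
- At 1330: 130 / 931 = 14.0%.
- The rule covers both outcomes, so there is a matching upper limit (100% − 14.3% = 85.7% at 1300). It is far from any rate in the documents.

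**Step 5: does the Addendum settle it?** It derives 1330 from the number of patients not recommended for care whom it wants in the validation sample. It makes no count of training cases per variable.

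**The case against.** The strongest reply is that little practical effect remains. The 10% is deliberately conservative and lies below the plan's own pilot rate. At the pilot rate the gap is 124.7 cases against 130. At the newer 50% rate the rule is exceeded by a wide margin, and the Addendum presents its conservative target as a buffer. All of this stands, and it is why the point is minor. It does not make the Sample Size paragraph correct at 10%, which is the figure it uses. The Addendum also makes the 50% conditional on the early findings holding, and names selection bias as a likely contributor.

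A second reply is that the split and the training-only fit are disclosed in the very next paragraph. That is fair: the fault is an unadjusted calculation, and nothing is concealed.

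A third is that 1300 might be the derivation cohort alone, because Section 2, Aim 2 speaks of validation in a separate cohort. This reading is weak. The Data Analysis paragraph and the Addendum both take the training and validation groups out of the overall cohort.

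Finally, ten per variable is only a rule of thumb. The check here holds the plan to its own stated minimum. It does not endorse that number as sufficient for stepwise selection.

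**Conclusion.** The text is wrong as written, and the matter is minor. At 10% prevalence, 1300 meets the stated minimum only when the whole cohort is counted. The training group is expected to hold 91 cases (7.0 per variable), or about 93 (7.2) at 1330. The gap is trivial at 13.7% and absent at 1300 or 1330 if 50% holds.

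A reader might infer that the model is bound to be underpowered, or that the study needed 130 / (0.70 × 0.10) = 1857.1, so 1858 patients. The documents do not support either. Both inferences treat a deliberately low planning value as the true rate, whereas both observed rates that the Sample Size paragraph and the Addendum report are higher, and the latest is far higher. The defect lies in the justification and is not shown to exist in the realised data.

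The conclusion rests on the plan's count of 13 variables, its own threshold of 10, and a training group with the same prevalence as the cohort. The figures are expected counts; the realised ones will vary.

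**What to change.** In Section 3A, Aim 2, Sample Size, state three things:

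- 1300 meets the 10-per-variable rule at 10% prevalence only for the whole cohort.
- Under the 70/30 split, the training group is then expected to hold 91 cases, or 7.0 per variable.
- At N = 1300 the rule is met in the training group only if prevalence is at least about 14.3%.

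Make the Sample Size entry in the Protocol Summary consistent with this. In the analysis, report the realised number of training patients per variable for each outcome and whether it reaches 10.

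Keep the 70/30 split and add no patients. The ratio at 1330 should not be written in as settled: the Addendum seeks about 400 patients not recommended for care in the validation sample, but 30% of 1330 is 399 patients in all. That needs its own reconciliation.

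The cost is a few sentences and one reported count per outcome, with no new data. The drawback is a less favourable stated ratio at 10%. The Addendum says that the final two-week follow-up was completed in September 2022, so the realised counts are the most useful part of the change; they can still be reported now that recruitment has ended.

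### The single 70/30 split makes Aim 2's main accuracy estimate noisier than the data allow; a bootstrap on the whole triage cohort would cut AUC error by a factor of about 1.6 to 1.8

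*Combined protocol and SAP*

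**What the plan says.** The Data Analysis text for Aim 2 (section 3, under Primary Outcomes) sets up the split: "Data from the prospective cohort will be divided into training and validation groups (70% and 30% of the overall cohort respectively". The model comes from the larger part only: "Stepwise multiple regression with bidirectional elimination will be used on the training group dataset". Questions that do not contribute there are dropped from the tool. Accuracy then comes from the smaller part only: "The resultant model will be applied to data from the validation cohort", with calibration and ROC curves calculated in that group. The cut-off is to favour sensitivity, but no numeric target is given.

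The Addendum, in its adjusted sample-size paragraph, repeats the split: "Data collected from our prospective cohort will be divided into training and validation groups (70% and 30% of the overall cohort respectively". It also ties the revised sample sizes to the validation part.

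The documents describe no bootstrap or k-fold procedure and no refit on all patients. They do not say whether patients are assigned to the two parts at random, by date or by site. Aim 2 in section 2 promises validation in different patients; in the analysis plan the only such group is the 30% of the same cohort.

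**The concern.** The study is sized for Aim 2, and the accuracy of the triage tool is its main result. With one split, that result depends on which patients fall in the 30% and on how many of them need care. The same 30% never inform the choice of items or their weights. Fitting on everyone and correcting for optimism by bootstrap uses every patient for both purposes. What is at stake is chiefly the precision of the reported AUC. The point does not rest on the number of cases per variable, or on whether the validation is external.

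**Working it through.** **Inputs from the documents.** 13 candidate variables ("The preliminary triage instrument has 13 variables derived from 7 questions"); the sizing rule ("A minimum sample size of 10 participants per variable per potential model outcome"); the planning prevalence and target ("Conservatively estimating that 10% of contacted patients will require further care, a sample size of 1300 patients in the triage cohort will be targeted"). The Addendum gives 1330 patients at 10% prevalence, or 730 at 50%, with about 400 or 220 patients required in the validation sample.

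**The plan's own figures.** 13 × 10 / 0.10 = 1300, as stated. 400 / 0.30 = 1333 and 220 / 0.30 = 733, close to the stated 1330 and 730. The Addendum's sizes therefore depend on the 30% part.

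**What the split leaves** (N × 0.7 or N × 0.3, times prevalence), with the 95% half-width for an assumed AUC of 0.80 (1.96 × Hanley-McNeil standard error):

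| N, prevalence | Training cases | Validation cases / non-cases | Half-width, 30% | Half-width if all N were independent test data |
|---|---|---|---|---|
| 1300, 10% | 91 | 39 / 351 | 0.086 | 0.047 |
| 730, 50% | 255.5 | 109.5 / 109.5 | 0.059 | 0.032 |
| 1330, 50% | 465.5 | 199.5 / 199.5 | 0.043 | 0.024 |

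For 1300 at 10%, an assumed AUC of 0.70 gives 0.095 against 0.052, and 0.90 gives 0.066 against 0.036. The last column is an ideal: 1 / √0.3 = 1.83 is roughly the most that could be gained. A bootstrap reuses the fitting data, so its real gain has to be simulated.

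**Simulation.** Each cohort was analysed in two ways: selection on a random 70% and testing on the 30%; or selection on everyone with an optimism-corrected bootstrap that repeats the selection in each resample. Each estimate was compared with the true AUC of its own model in a large new sample.

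- Run A: 160 cohorts per scenario, 13 correlated binary items, backward selection at 5%, 40 resamples.
- Run B: 240 cohorts, bidirectional stepwise selection as planned, 40 resamples. Assumed item frequencies were 10% to 30%, with latent correlation 0.25. Log odds ratios were 1.2, 0.8, 0.6, 0.5, 0.5, 0.4, 0.3, 0.3 and 0.2, with four null items.
- Run C: a further run on the same scenarios.

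Root-mean-square error of the AUC estimate, hold-out against bootstrap (ratio):

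| N, prevalence | Run A | Run B | Run C |
|---|---|---|---|
| 1300, 10% | 0.037 v 0.022 (1.68) | 0.0435 v 0.0262 (1.66) | 0.043 v 0.024 (1.79) |
| 730, 50% | 0.035 v 0.019 (1.84) | 0.0344 v 0.0208 (1.65) | 0.036 v 0.021 (1.71) |
| 1330, 50% | 0.023 v 0.014 (1.64) | not run | 0.023 v 0.014 (1.64) |

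Ratios of 1.6 to 1.8 are variance ratios of 1.6² = 2.6 to 1.8² = 3.2. The relative Monte Carlo error of a root-mean-square error from R cohorts is about 1/√(2R): 5.6% for 160 and 4.6% for 240. The spread between runs is therefore not meaningful.

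**Bias.** In run B the mean AUC error was −0.003 (10%) and +0.007 (50%) for the hold-out, and −0.002 and +0.005 for the bootstrap. The uncorrected AUC on the fitting data was too high by 0.018 and 0.024, which is why selection must be repeated inside each resample.

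**The tool itself.** In run B the true AUC was 0.735 on all patients against 0.728 on 70% (1300, 10%), and 0.681 against 0.675 (730, 50%). Across runs the gain was 0.004 to 0.008. In run B the all-patient model was better in 78% to 81% of cohorts.

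**Sensitivity at a cut-off set for 90%.** Run B gave errors of 0.020 v 0.019 (1300, 10%) and 0.009 v 0.006 (730, 50%), dominated by tied scores. Run C gave about 0.010 v 0.007 to 0.009 at 50%. At 10% the runs do not agree on the size of any gain. For scale, exact 95% intervals on the hold-out alone are 82.7% to 99.4% for 37/39 (10% prevalence), 88.5% to 98.0% for 104/110, and 91.0% to 97.6% for 190/200 (both 50%).

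**The case against.** A hold-out is simple, honest and already specified, and section 2 promises validation in separate patients. If the 50% prevalence in the Addendum persists, the hold-out has about 110 to 200 cases, and at 1330 patients the AUC error differs by only 0.023 − 0.014 = 0.009. No decision in the protocol is shown to turn on that. A split by site or date would also test transportability, which a bootstrap does not replace.

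Much of this stands. The split is not an error, and its estimate is not materially biased. But the ratio is much the same at both prevalences, and the Addendum keeps the larger target as a conservative choice, so 10% has not been withdrawn. If the split is random, the 30% gives internal validation too. Keeping it as a secondary check loses nothing.

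Three stronger readings are tempting and are not supported:

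- A reader might set 124/130 (exact interval 90.2% to 98.3%) beside 37/39 and infer that the bootstrap delivers that precision for sensitivity. It does not: 124/130 would be an apparent figure on the patients used to fit the model and choose the cut-off, and the simulations show little gain or an uncertain one.
- A reader might infer a clearly better tool. The gain in AUC is under 0.01.
- A reader might take the training count as proof that the model is under-sized. At 10% prevalence it is 91/13 = 7.0 cases per variable, against the plan's minimum of 10. At 50% it is 19.7 (730 patients) or 35.8 (1330). That is a separate question and depends on prevalence.

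**Conclusion.** The point holds as one of efficiency. The plan reports its main accuracy result from 30% of the patients in one partition, and the AUC error is about 1.6 to 1.8 times what an optimism-corrected bootstrap on the same patients would give. The gain in the tool's true AUC is very small (0.004 to 0.008). The gain for sensitivity, which the plan puts first, is uncertain at 10% prevalence and small at 50%.

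These sizes rest on assumed item effects, frequencies and correlation, and on a random split, which the documents do not specify. The direction agreed in every scenario run. This is an inexpensive improvement; the documents do not support calling the planned validation invalid.

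**What to change.** Fit the final model on the whole triage cohort. Report optimism-corrected AUC, calibration, sensitivity and specificity, with intervals, from a bootstrap (for example 500 resamples) that repeats the full stepwise selection and the cut-off choice in each resample. This requires a fixed entry and removal threshold and a fixed cut-off rule; the plan gives neither. Keep the 70/30 result as a secondary check, and state how patients are assigned to the two parts.

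The cost is analysis-plan wording and computing time, with no new data. There are three downsides:

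- The headline becomes an optimism-corrected internal estimate, which needs a sentence of explanation and should not be called external validation.
- The Addendum's sample-size paragraph is tied to the 30% sample and must be restated.
- The Addendum reports that the last two-week follow-up was in September 2022. The change should therefore be recorded as made before outcome data were examined, or labelled as a later change.

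### Stepwise, significance-based selection without shrinkage tends to make the triage tool's risks too extreme and can cost a few points of specificity at high sensitivity

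*Combined protocol and SAP*

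**What the plan says.** The plan is in the protocol, Aim 2, under Primary Outcomes (Sample Size and Data Analysis).

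- Candidates: "The preliminary triage instrument has 13 variables derived from 7 questions".
- Size: "A minimum sample size of 10 participants per variable per potential model outcome" is taken as the requirement, and "Conservatively estimating that 10% of contacted patients will require further care, a sample size of 1300 patients in the triage cohort will be targeted".
- Split: "Data from the prospective cohort will be divided into training and validation groups (70% and 30% of the overall cohort respectively").
- Model: "Stepwise multiple regression with bidirectional elimination will be used on the training group dataset", followed by "Survey questions that are found not to contribute significantly to prediction will be dropped from the final triage tool".
- Operating point: "risk cutoffs will target a highly sensitive test with minimal false negatives".

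Calibration is judged by the mean error between predicted risk and the physician's decision in the validation group, and discrimination by ROC curves. The text gives no entry or removal threshold, no shrinkage, no calibration slope and no numerical sensitivity target. It does not say whether selection acts on the 13 variables or on the 7 questions.

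The Addendum (Supplement Sample Size Calculations Adjustment) keeps the 70/30 split and raises the target to 1,330. It reports that newer multicentre data put the proportion needing care at 50%, and gives 730 as the target if that persists.

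**The concern.** The final questionnaire and its risk score are the product of Aim 2. Three features of the plan bear on their quality.

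First, significance in a training set of limited size is a poor guide to an item's predictive value. Weak but real predictors are dropped for lack of power. Second, coefficients that survive selection, with no shrinkage afterwards, tend to be too large, so predicted risks are too extreme. Third, the one calibration measure planned may not show this.

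Because the tool is meant to run at high sensitivity, information lost by dropping items is paid for in specificity at that sensitivity. The Addendum sizes the validation sample on specificity, and a tool that refers nearly everyone does not triage.

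**Working it through.** **1. The plan's own figure.** N = variables × 10 ÷ proportion needing care = 13 × 10 ÷ 0.10 = 1,300. This reproduces the target.

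**2. The same rule in the training group.** The model is fitted on 70% of the cohort only.

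| Cohort | Rate | Training n | Needing care | Per variable (÷ 13) |
|---|---|---|---|---|
| 1,300 | 10% | 910 | 91 | 7.0 |
| 1,300 | 13.7% | 910 | 124.7 | 9.6 |
| 1,330 | 10% | 931 | 93.1 | 7.2 |
| 730 | 50% | 511 | 255.5 | 19.7 |
| 1,330 | 50% | 931 | 465.5 | 35.8 |

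The 13.7% is the pilot rate ("physician exams leading to a recommendation for further care occur for 13.7% of calls"). The rule is missed in training at 10% and narrowly at 13.7%. It is met comfortably at 50%.

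**3. Simulation.** The documents give no item frequencies or effects, so these are assumptions:

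- 13 binary items with prevalence 0.10 to 0.35 and latent correlation 0.2.
- Bidirectional stepwise logistic regression at p < 0.05, against ridge logistic regression on all 13 items with the penalty from 10-fold cross-validation.
- 200 replicates per setting, each evaluated on 40,000 new subjects.

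Four signal patterns give the range. Cells show specificity at 95% sensitivity, stepwise → ridge, with both methods read at the same sensitivity.

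| Pattern | 910 at 10% | 511 at 50% | 931 at 50% |
|---|---|---|---|
| A: all 13 items moderate (log-odds ratio 0.45) | 0.175 → 0.210 | 0.126 → 0.172 | 0.151 → 0.178 |
| C: 4 strong, 9 weak (0.25) | 0.257 → 0.285 | 0.142 → 0.172 | 0.154 → 0.186 |
| B: 5 strong, 8 null | 0.219 → 0.224 | 0.137 → 0.141 | 0.145 → 0.144 |
| D: 3 strong, 10 null | 0.217 → 0.215 | 0.127 → 0.127 | 0.127 → 0.126 |

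Before rounding, the gain is about 2.8 to 4.5 points in A and C, and -0.2 to +0.4 in B and D. At 90% sensitivity the gain in C is 1.2, 3.5 and 1.9 points. Stepwise dropped on average 3.5 to 7.3 truly predictive items in A and C, and 0.0 to 0.4 in B and D.

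**4. Where the gain comes from.** In C an unpenalised model on all items already reaches 0.279, 0.164 and 0.182. Most of the specificity gain therefore comes from keeping the items. The penalty mainly corrects the slope: the unpenalised full model has slopes 0.899, 0.866 and 0.936 there, and ridge 1.091, 1.068 and 1.055.

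**5. Calibration.** Mean stepwise slope was 0.78 to 0.96 over the twelve settings, and below 0.9 in 24 to 92% of replicates. Ridge gave 1.03 to 1.11, and was below 0.9 in 6 to 16%. A further 13-item run gave 0.81 to 0.98 for stepwise and 1.01 to 1.14 for ridge. If mean error is the average of predicted minus observed, over- and under-prediction cancel. In a random split it can then be near zero while the slope is well below 1.

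**6. False negatives.** With the cutoff set in the training data for 95% sensitivity, stepwise reached sensitivity 0.97 to 1.00 in new data, at specificity 0.00 to 0.14. Ridge reached 0.94 to 0.99, at specificity 0.05 to 0.31.

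**The case against.** **Stronger readings.** A reader might infer that dropping questions by significance works against the aim of few false negatives. The documents do not support this: the plan pursues that aim through the risk cutoff, and in step 6 it was ridge, not stepwise, that sometimes fell slightly below 95%.

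A reader might also infer a much larger loss. One simulation with 12 items showed gaps of 3 to 15 points at 90% sensitivity, for example 0.091 against 0.238 at the 50% rate. A test unrelated to the outcome has specificity 0.10 at 90% sensitivity, so 0.091 cannot be a fair reading at that point. Few items give few distinct scores, which push stepwise to a higher sensitivity than the one named. A 40-replicate check confirmed this: without interpolation, stepwise ran at an actual sensitivity of 0.94 to 1.00. At equal sensitivity the gains were 0.5 to 6.2 points at 90% and 0.3 to 5.4 at 95%. The coarse score is a real practical limit, but it is a different matter from the loss at equal sensitivity.

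**What else stands.**

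- The plan regards the harm of a false positive as minimal, so a few points of specificity are a modest loss.
- If few items carry the signal, ridge gains nothing, and its error in predicted risk is higher (by 0.002 to 0.022; in A and C it is lower by 0.012 to 0.047).
- Ridge overshoots slightly. Mean distance of the slope from 1 changed by -0.072 to +0.034, so it does not improve in every setting.
- The p < 0.05 threshold is assumed. A looser one (p < 0.157) fell between the two methods in pattern C: 0.271, 0.151 and 0.164.
- If selection is by whole question, an option such as fever is lost only if all of question 6 goes. That reading was not simulated.
- At the 50% rate overfitting matters less. The loss from dropping weak items remains, at 3.0 to 3.2 points in C.
- A shorter telephone tool has value, and an all-item model gives some of it up.

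On which pattern applies, Triage Tool Development says an expert panel had already removed questions of marginal value. That makes spread signal plausible but does not establish it.

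**Conclusion.** The concern holds as a conditional one. The training group misses the plan's own events-per-variable rule at its planning rate (7.0 against 10), though not at the 50% rate. Stepwise selection without shrinkage is over-extreme on average (simulated slope about 0.8 to 0.98), and the planned check may not reveal it. The cost is specificity at the chosen sensitivity: about 1 to 5 points at 90-95% sensitivity if many items carry signal, and about 0 if only a few do. These sizes rest on assumed item frequencies, effects, correlation and selection threshold. What does not depend on the item effects is that the plan leaves the selection threshold, sensitivity target and calibration slope unstated.

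**What to change.** Replace the stepwise and question-dropping sentences in Aim 2, Data Analysis, with wording such as:

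*A logistic model containing all 13 triage variables will be fitted in the training group with a ridge or elastic-net penalty chosen by 10-fold cross-validation. The target sensitivity is [value]. A question will be removed only if cross-validated specificity at that sensitivity falls by no more than [tolerance]. In the validation group, calibration slope and intercept will be reported with the ROC curve.*

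The team should choose one penalty and put numbers in both brackets; without them the removal rule cannot be carried out.

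**Cost.** Wording and standard software, with no new data. The tool may stay at seven questions and need a simple score calculator, for example in REDCap. The penalised slope may slightly exceed 1. The Addendum says the last two-week follow-up was completed in September 2022, so the change must be dated and documented as made after data collection. If the validation results have not yet been examined, the change should be fixed before they are.
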